### 2.3.2. Benefit assessment

This study is being conducted in healthy female participants of non-childbearing potential with no significant medical history. Participants will not receive benefit from this study.

### 2.3.3. Overall benefit-risk conclusion

Overall, the available data from non-clinical and clinical studies has not identified prohibitive risks associated with GSK3036656 at the exposures planned for this study. While there are a number of important potential risks identified for GSK3036656, these can be addressed in clinical trials with proper participant selection, close safety monitoring, and specific risk characterization and mitigation.

## 3. OBJECTIVES, ENDPOINTS AND ESTIMANDS

The study objectives and endpoints are presented in [Table 3](#)

**Table 3 Objectives and Endpoints**

Objective(s)	Endpoint(s)
Primary	
To assess the effect of steady state exposure of GSK3036656 on the single dose PK of EE and LNG in healthy female participants of non-childbearing potential	Area under the plasma concentration-time curve to infinity AUC(0-inf) and maximum observed concentration (C max ), after a single dose of EE and LNG (EE AUC (0-inf) , EE C max , LNG AUC (0-inf) , LNG C max )
Secondary	
To characterize the steady state PK of GSK3036656 in the presence of EE/LNG	AUC(0- $\tau$ ), C max , C t (Day 8, 10, 12, 15 and 16) and time of maximum observed concentration (T max ) for GSK3036656
To characterize the single dose PK of EE/LNG alone and in the presence of GSK3036656	AUC(0-t), T max and t 1/2 for EE and LNG, in Treatment Period 1 and Treatment Period 3.
To assess the safety and tolerability of GSK3036656 and Microgynon when given alone or in combination in healthy female participants of non-childbearing potential	
 
• Incidence of SAEs within each treatment period.
 
• Incidence of AEs of grade 3 severity or higher within each treatment period.
 
• Incidence of AEs considered by the investigator to be possibly, probably, or definitely related to study drug within each treatment period (overall and separately for relationship to Microgynon and to GSK3036656).
 
• Incidence of participants withdrawn from the treatment/study due to adverse events within each treatment period.
 

Objective(s)	Endpoint(s)
	
 
Incidence of ECG values PCI within each treatment period.
 
Incidence of clinical chemistry laboratory values of PCI within each treatment period.
 
Incidence of hematology laboratory values of PCI within each treatment period.
 
Incidence of vital signs parameters of systolic blood pressure (SBP), diastolic blood pressure (DBP) and heart rate (HR) of PCI within each treatment period.
 

## PRIMARY ESTIMAND

The primary clinical question of interest is:

What is the effect of treatment with GSK3036656, estimated by the point estimate and 90% confidence interval (CI) for the ratio of the geometric mean of Microgynon+GSK3036656 compared to Microgynon (within participant comparison), on the exposure (AUC(0-inf) and Cmax) of EE and LNG in healthy female participants who are missing no more than one 20 mg dose of GSK3036656 in treatment period 2 and are 100% compliant with study treatments in treatment periods 1 and 3?

The estimand is described by the following attributes:

- Population: Healthy female participants of non-childbearing potential aged 18 to 65 years.
- Endpoints: Plasma PK parameters of EE and LNG: AUC(0-inf) and Cmax.
- Treatments: single dose Microgynon +14 days GSK3036656 (Treatment Period 3) Vs single dose Microgynon alone (Treatment Period 1)
- Strategy for intercurrent event: The intercurrent events of interest are participants missing dose of Microgynon in treatment periods 1 and 3, missing dose of GSK3036656 in treatment period 3, or missing more than one 20 mg dose of GSK3036656 in treatment period 2. The strategy for handling all of these intercurrent events will be a Principal Stratum Strategy, where we are only interested in the strata of participants who are missing no more than one 20 mg dose of GSK3036656 in treatment period 2 and are 100% compliant with study treatments in treatment periods 1 and 3.
- Population-level summary: The point estimate and 90% CI for the ratio of the geometric mean for each of EE AUC(0-inf) , LNG AUC(0-inf) , EE Cmax and LNG Cmax, for Microgynon+GSK3036656 (Treatment Period 3) compared to Microgynon alone (Treatment Period 1) (within participant comparison).

Rationale for estimand: Interest lies in estimating the effect of GSK3036656 on the pharmacokinetics of Microgynon, which cannot be accurately assessed in the situation where participants are missing more than one 20 mg dose of GSK3036656 in treatment period 2 and are not 100% compliant with study treatments in treatment periods 1 and 3.

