## 4. STUDY DESIGN

### 4.1. Overall design

This is a Phase 1, open-label, fixed-sequence, 1-way DDI study designed to assess the PK, safety, and tolerability of GSK3036656 and an oral contraceptive containing EE/LNG (Microgynon) when the oral contraceptive is administered alone and in combination with GSK3036656 in healthy female participants of non-childbearing potential.

The study consists of a screening period, check-in to the inpatient facility for a single dose treatment period with Microgynon given alone followed by PK assessments for 72 hours, then discharge. The participant immediately starts a 14-day treatment period with GSK3036656 and is readmitted to the clinic on Day 15 where they receive a single dose of Microgynon in combination with GSK3036656. The participant is discharged from the clinic on Day 18 following completion of the 14-day GSK3036656 treatment period and the 72 hour EE/LNG PK assessments.

Participants will be screened within 14 days before the start of Treatment Period 1. The treatments are as follows:

- Treatment Period 1: Microgynon (0.03 mg EE/0.15 mg LNG) single dose on Day 1 of the treatment period.
- Treatment Period 2: A loading dose of GSK3036656 40 mg on Day 4 then GSK3036656 20 mg od from Day 5 to Day 14
- Treatment Period 3: Microgynon (0.03 mg EE/0.15 mg LNG) single dose coadministered with GSK3036656 20 mg on Day 15 of Treatment Period 3, then GSK3036656 20 mg od alone from Day 16 to Day 17.

Participants will take the single dose of Microgynon in the morning after an overnight fasting (at least 8h) at approximately the same time in Treatment Periods 1 and 3. Participants should remain fasted until at least 4 hours post dose.

Time of dose administration for GSK3036656 should be approximately 24 hours apart.

Blood samples for the analysis of EE, LNG and GSK3036656 will be collected as per SoA.

Safety and tolerability will be assessed by monitoring and recording of AEs, clinical laboratory test results, vital sign measurements, 12-lead ECG results, and physical examination findings.

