## 4.3. Justification for dose

The daily clinical dose of 20 mg of GSK3036656 was selected based on evaluation of the final efficacy data from the completed monotherapy early bactericidal activity study with GSK3036656. Exposure-Response analysis was utilised to determine the clinical steady-state exposure associated with >90% of response (change from baseline in logCFU) and this was set as the targeted clinical exposure. Furthermore, a probabilistic analysis (PTA%) using both inter-subject variability and parameters' uncertainty was conducted to ensure that >90% of patients would achieve the targeted clinical exposure.

Based on this, a daily repeat dose of 20 mg of GSK3036656 will be used in the current study with a loading dose of 40 mg on Day 4 administered to ensure a PK profile that closely resembles steady-state by Day 8 of Treatment Period 2, thus allowing one week (from Day 8 to Day 15) for a potential enzyme induction to occur, while maintaining a 14-day cycle of GSK3036656 administration.

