## 4.2. Primary Endpoint(s) Analyses

The primary objective of this study is to assess the effect of steady state exposure of GSK3036656 on the single dose PK of EE and LNG in healthy female participants of non-childbearing potential aged 18 to 65 years, who are missing no more than one 20 mg dose of GSK3036656 in treatment period 2 and are 100% compliant with study treatments in treatment periods 1 and 3. For the analyses planned in the following section, the potential intercurrent events that will be considered are participants missing a dose of Microgynon in treatment periods 1 and 3, or missing dose of GSK3036656 in treatment period 3, or missing more than one 20 mg dose of GSK3036656 in treatment period 2. Events leading to missing data are: participant withdrawal from study/ loss to follow-up, or missing PK assessments.

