### 6.2.4. Study Period

Assessments and events will be classified according to the time of occurrence relative to the study intervention period.

Treatment period 1 ranges from Day 1 dose to Day 4 predose, similarly treatment period 2 ranges from Day 4 dose to Day 15 predose and treatment period 3 ranges from Day 15 dose until Day 18.

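### The Period 2 compliance rule counts missed 20 mg doses but ignores their timing, so a participant who missed only the Day 14 dose is analysed as if at steady state on Day 15

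*Protocol*

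**What the plan says.** The primary objective (Protocol Table 3) is "To assess the effect of steady state exposure of GSK3036656 on the single dose PK of EE and LNG". The primary estimand in Protocol section 3 restricts the analysis to participants who are "missing no more than one 20 mg dose of GSK3036656 in treatment period 2" and fully compliant in Periods 1 and 3. The matching intercurrent event for Period 2 is "or missing more than one 20 mg dose of GSK3036656 in treatment period 2". SAP 1.1 repeats this, and SAP 4.2 again names "missing more than one 20 mg dose of GSK3036656 in treatment period 2" as the event. The same Period 2 limit defines the estimand for steady-state GSK3036656 PK.

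The Period 2 regimen is "A loading dose of GSK3036656 40 mg on Day 4 then GSK3036656 20 mg od from Day 5 to Day 14" (Protocol 4.1). SAP 6.2.4 sets the boundary: "treatment period 2 ranges from Day 4 dose to Day 15 predose". The Day 14 dose and the loading dose therefore both sit in Period 2, outside the full-compliance requirement. Protocol 4.3 gives the purpose of the loading dose as "to ensure a PK profile that closely resembles steady-state by Day 8 of Treatment Period 2", which leaves a week for any induction.

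Neither document says which 20 mg dose may be missed, or how a missed 40 mg dose counts. Protocol 9.3.2.3 and SAP 4.2.3 plan no sensitivity analysis of the primary endpoints.

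**The concern.** The rule is meant to select participants in whom GSK3036656 is at steady state when Microgynon is given on Day 15. A count does not do that, because the effect of a missed dose on Day 15 depends on how recent it was. Missing Day 17, two days after Microgynon, removes a participant. Missing Day 14, the day before, does not.

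The last scheduled visit before readmission is Day 12 (Schedule of Activities), so the Day 14 dose is normally taken at home. Compliance there rests on questioning, capsule count and diary (Protocol 6.4).

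Two things are at stake. The secondary steady-state values (Day 15 trough, AUC(0-τ), Cmax) would include a participant who is not at steady state, as would the trough model that SAP 4.3.1.2 uses to judge whether steady state was reached. For the primary comparison, lower exposure to the perpetrator would pull any interaction toward a ratio of 1. Success is a 90% CI inside 0.80-1.25, so the error lies on the side of declaring no interaction.

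**Working it through.** **1. The plan's own power figure.** Inputs are from Protocol 9.5: CVw 11.5, 12.5, 14.9 and 17.9%, true ratio 1.0, correlation 0.6, n = 16, limits 0.80-1.25, α = 0.05 per one-sided test. With σw² = ln(1 + CV²), SE = σw·√(2/n) and n − 2 degrees of freedom, the power for LNG Cmax is 91.6% (stated 92.73%). Joint power, by simulation of four correlated endpoints, is 90.7% (stated 91.91%). Both agree within about 1.3 points. The same calculation gives 87.8% at n = 15, 84.2% at 14 and 79.4% at 13.

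**2. Effect of a missed Day 14 dose on GSK3036656.** The half-life is not in the documents, so 12 to 72 h is an assumption. Use one-compartment superposition with 24 h dosing and rapid absorption, and let r = 2^(−24/t½). At steady state, relative to full dosing:

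- Day 15 predose trough: the missed dose would have contributed D·r to a trough of D·r/(1 − r), so the loss is 1 − r.
- Day 15 AUC(0-τ): the missed dose would have contributed a fraction r(1 − r). The same fraction applies to Cmax.

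| Assumed t½ (h) | r | Trough loss, 1 − r | AUC(0-τ) loss, r(1 − r) |
|---|---|---|---|
| 12 | 0.250 | 75% | 19% |
| 24 | 0.500 | 50% | 25% |
| 36 | 0.630 | 37% | 23% |
| 48 | 0.707 | 29% | 21% |
| 72 | 0.794 | 21% | 16% |

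Running the actual schedule (40 mg on Day 4, ten 20 mg doses) gives nearly the same. At 72 h the Day 15 trough falls from 94.2% to 73.5% of steady state, a 22% loss.

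**3. Does the count track distance from steady state?** At a 24 h half-life:

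| Pattern | Status under the rule | Day 15 trough, % of steady state |
|---|---|---|
| Missed Days 5 and 6 | excluded | 99.7 |
| Missed Day 9 only | kept | 98.4 |
| Missed Day 14 only | kept | 50.0 |

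It does not.

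**4. Exposure over the 72 h EE/LNG profile.** The participant still takes GSK3036656 on Days 15 to 17. Her loss of GSK3036656 AUC over those 72 h is r(1 − r³)/3: 8.2% at 12 h, 14.6% at 24 h, 15.7% at 36 h, 15.2% at 48 h and 13.2% at 72 h. The effect on the EE/LNG ratio does not follow from this, because the documents give no exposure-interaction relation.

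**5. Missed loading dose.** Day 15 trough as % of steady state at 12/24/36/48/72 h: 100/99.9/99.0/96.9/90.1 without the loading dose, against 100/100/99.7/98.7/94.2 with full dosing. On Day 8 the figures are 98/87.5/75/65/50 without it, against 101/100/93.5/85/71 with it.

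**6. Existing safeguards.** SAP 4.3.1.2 fits Day 8, 10, 12 and 15 predose troughs at group level and removes no individual. SAP Table 3 takes trough values directly from the observed data. The Schedule of Activities requires the Day 8, 10 and 12 samples to be 24 h after the previous dose. A sample that follows a missed dose fails that definition, but no analysis rule removes it.

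**The case against.** The strongest reply is that the primary result would hardly move. In-vitro data suggest a low interaction risk (Protocol 2.1 and 2.2), and GSK3036656 is still taken with Microgynon on Day 15 and on the next two days. As an illustration, suppose the true ratio is 0.75 and three of 16 participants each lose a quarter of the log effect. The estimate becomes exp[ln 0.75 × (1 − 3/16 × 0.25)] = 0.760. Three is itself generous: if all 16 missed exactly one of the ten 20 mg doses at random, 16 × 1/10 = 1.6 would be expected to miss Day 14. This stands. The case for change rests mainly on the steady-state GSK3036656 summaries and on the logic of the stratum.

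The case would also be visible. Concentrations are listed, compliance is summarised, and a low Day 15 trough would push the modelled slope down. A Schedule of Activities footnote allows early admission around Day 14, which could make that dose supervised. But visibility is not an analysis rule, and early admission is optional.

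A reader might go further and infer that a participant without the 40 mg dose is analysed as being at steady state when she is not. The documents do not support that. The wording is ambiguous: the capsule strength is 20 mg (Protocol Table 4), so 40 mg is two units and can be read as exceeding a one-dose tolerance. The Day 4 dose follows clinic procedures, including an ECG within 15 minutes before dosing, so a miss is unlikely. Even without it, the Day 15 trough is 96.9% of steady state or more for half-lives up to 48 h. What is lost is part of the Day 8 to 15 lead-in for induction.

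**Conclusion.** The point holds for the Day 14 dose. On any reading of the rule, a participant who missed only that dose stays in the primary stratum and in the steady-state GSK3036656 estimand. Over an assumed half-life of 12 to 72 h, her Day 15 trough is about 21-75% lower and her AUC(0-τ) 16-25% lower than with full dosing. These figures rest on one-compartment superposition and on that assumed range.

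For the EE and LNG ratios only the direction can be stated: toward no interaction, provided that any interaction grows with exposure. The size cannot be computed and is probably small. A reader might infer that the equivalence conclusion is materially biased, or that several participants will be affected. The documents give no basis for either. Nor do they support extending the timing rule to Day 13. The loading dose is a matter of clarification.

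**What to change.** In Protocol 3 and 9.3.2.3, and SAP 1.1, 4.2.3 and 4.3.1.2:

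1. Pre-specify a sensitivity analysis of the four primary endpoints excluding participants who missed the Day 14 dose, or exclude them from the primary stratum.
2. Exclude from the trough summaries and the trough-slope model any sample not preceded by a dose about 24 h earlier. After a missed Day 14 dose, also exclude Day 15 AUC(0-τ) and Cmax from the steady-state summary.
3. State that, for the analysis, a missed 40 mg loading dose exceeds the tolerance of one 20 mg dose.

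The sensitivity analysis costs only analysis work. If the stratum is tightened instead, the first exclusion from 16 evaluable costs 90.7 − 87.8 = 2.9 points of joint power, and a second costs 87.8 − 84.2 = 3.6. The cost is smaller if the roughly 20 enrolled leave more than 16 evaluable. Settling this before the data are seen avoids a judgement made with the concentrations in view. No change to dosing is implied.

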### **Primary estimands of secondary Pharmacokinetic endpoints**

#### **Steady State PK of GSK3036656**

The clinical question of interest is:

What are the estimates (mean/ median and variability) of steady state PK parameters (AUC(0- $\tau$ ), Cmax, C $\tau$  and Tmax) of GSK3036656 in the presence of EE/LNG in healthy female participants, who are missing no more than one 20 mg dose of GSK3036656 in treatment period 2 and are 100% compliant with study treatments in treatment period 3?

The Primary Estimand is described by the following attributes:

- Population: Healthy female participants of non-childbearing potential aged 18 to 65 years.
- Endpoints: AUC(0- $\tau$ ), Cmax, C $\tau$  and Tmax for GSK3036656
- Treatments: single dose Microgynon+14 days GSK3036656
- Strategy for intercurrent event: The intercurrent events of interest are participants missing their dose of Microgynon during treatment period 3, or missing a dose of GSK3036656 in treatment period 3, or missing more than one 20 mg dose of GSK3036656 in treatment period 2. The strategy for handling all of these intercurrent events will be a Principal Stratum Strategy, where we are only interested in the strata of participants who are missing no more than one 20 mg dose of GSK3036656 in treatment period 2 and are 100% compliant with study treatments in treatment period 3.
- Population-level summary:
  - For AUC(0- $\tau$ ), Cmax, and C $\tau$  of GSK3036656: Descriptive Statistics (including n, Arithmetic means with 95% CI, Geometric means with 95% CI, CV%, SD, Median with Min, Max);
  - for Tmax of GSK3036656: Descriptive Statistics (including n, Median with Min, Max).

Rationale for estimand: Interest lies in estimating the pharmacokinetics of GSK3036656 in the presence of Microgynon, which cannot be accurately assessed in the situation where participants are missing more than one 20 mg dose of GSK3036656 in treatment period 2 and are not 100% compliant with study treatments in treatment period 3.

## Pharmacokinetics of EE/LNG

The clinical question of interest is:

What are the estimates (mean/ median and variability) of the PK parameters (AUC(0-t), Tmax and t1/2) of EE and LNG with and without GSK3036656 in healthy female participants, who, for the estimates with GSK3036656 are missing no more than one 20 mg dose of GSK3036656 in treatment period 2 and are 100% compliant with doses of GSK3036656 in treatment period 3? For the estimates of PK parameters of EE and LNG taken alone, no intercurrent events are defined.

The Primary Estimand is described by the following attributes:

- Population: Healthy female participants of non-childbearing potential aged 18 to 65 years.
- Endpoints: AUC(0-t), Tmax, Cmax and t1/2 for EE and LNG
- Treatments: single dose Microgynon+ 14 days GSK3036656 and single dose Microgynon

Strategy for intercurrent event: The intercurrent events of interest, applicable to estimates of PK parameters for EE and LNG with GSK3036656 only, is participants missing one or more doses of GSK3036656 in treatment period 3, or missing more than one 20 mg dose of GSK3036656 in treatment period 2. The strategy for handling this intercurrent events will be a Principal Stratum Strategy, where we are only interested in the strata of participants who are missing no more than one 20 mg GSK3036656 dose in treatment period 2 and are 100% compliant with doses of GSK3036656 in treatment period 3. For the estimates of PK parameters of EE and LNG taken alone, no intercurrent events are defined.

- Population-level summary:
  - For AUC(0-t) and t1/2 (h) of EE and LNG: Descriptive Statistics (including n, Arithmetic means with 95% CI, Geometric means with 95% CI, CV%, SD, Median with Min, Max);
  - for Tmax of EE and LNG: Descriptive Statistics (including n, Median with Min, Max).

Rationale for estimand: Interest lies in estimating the pharmacokinetics of Microgynon, with and without GSK3036656. The PK of Microgynon taken with GSK3036656 cannot be accurately assessed in the situation where participants are missing more than one 20 mg dose of GSK3036656 in treatment period 2 or are not compliant with doses of GSK3036656 in treatment period 3.

**Primary estimand of secondary Safety endpoints****For all secondary safety endpoints the primary clinical question of interest:**

Are GSK3036656 and Microgynon, taken separately or together, safe and well tolerated in healthy female participants of non-childbearing potential aged 18 to 65 years, regardless of study treatment discontinuation and the level of compliance of either treatment?

The primary estimands for Safety are described by the following attributes:

**Adverse Events/ Serious Adverse Events, Clinical laboratory assessments, ECG, and Vital Sign measurements:**

- Population: Healthy female participants of non-childbearing potential aged 18 to 65 years.
- Endpoints:
  - Incidence of serious adverse events within each treatment period.
  - Incidence of adverse events of grade 3 severity or higher within each treatment period.
  - Incidence of adverse events considered by the investigator to be possibly, probably or definitely related to study drug (overall and separately for Microgynon and GSK3036656) within each treatment period.
  - Incidence of participants withdrawn from the treatment/study due to adverse events within each treatment period.
  - Incidence of ECG values of PCI within each treatment period.
  - Incidence of clinical chemistry laboratory values of PCI within each treatment period.
  - Incidence of haematology laboratory values of PCI within each treatment period.
  - Incidence of vital signs parameters of SBP, DBP and HR of PCI within each treatment period.
- Treatments: single dose Microgynon, once daily GSK3036656 and single dose Microgynon +once daily GSK3036656
- Strategy for intercurrent event: The intercurrent events of interest are participants missing the dose of Microgynon, missing one or more doses of GSK3036656 or discontinuing GSK3036656 early due to any reason. The strategy for handling these intercurrent events will be a Treatment Policy Strategy, where all safety data after the intercurrent event will be included.
- Population-level summary: Frequency and percentage of participants; with the denominator for percentages being the number of participants entering the treatment period.

Rationale for estimand: It is important to document all safety issues that could potentially be attributable to the regimen, regardless of treatment non-compliance/discontinuation.

